CLINICAL STUDY PROTOCOL

A Phase 2b/3 Open-label Trial of VTS-270 (2-hydropropyl- β -cyclodextrin) in Subjects with Neurologic Manifestations of Niemann-Pick Type C1 Disease Previously Treated Under Protocol VTS301

Regulatory Agency Identification Number: IND #113273

Protocol Number: VTS-270-302

Date of Protocol Amendment 2 Version 2: 10 February 2021

Date of Protocol Amendment 1 Version 1: 03 December 2019

Date of Original Protocol: 23 October 2018

Vtesse LLC, a Mallinckrodt Pharmaceuticals Company

[name]

[name]

SUMMARY OF CHANGES FOR PROTOCOL AMENDMENT 2

The Summary of Changes (SOC) reflects the changes made in Amendment 2 for VTS270-302 from Amendment 1 dated 03 December 2019. Key changes in Version 2.0 included updating the benefit / risk balance assessment of adrabetadex to negative, resulting in a recommendation effective 20 January 2021 that treatment with adrabetadex be discontinued as soon as possible with appropriate clinician oversight. In recognition of the complexity of patient care, Mallinckrodt will make adrabetadex available for up to 9 months to allow time for the physician and patient/family to develop a transition plan. Continued treatment with adrabetadex is contingent upon a discussion between the treating physician and patient/family and re-consent. Likewise, continuation of treatment is also contingent upon approval by the respective Institutional Review Board (IRB) / Ethics Committee (EC) and health authority. The study objectives/endpoints/outcome measures were revised to delete all efficacy assessments and their analysis. A full description of the changes to this amendment can be found in the Summary of Changes document for VTS302 protocol amendment 2. A high-level description of the changes includes the following:

1. The benefit / risk information was updated to state that the sponsor has made a determination that the benefit / risk balance was negative.
2. Treatment with adrabetadex may be continued until 20 October 2021 as needed to allow time to start alternative treatment unless there are additional time restrictions mandated by an IRB/EC or health authority. Subjects may stop treatment at any time before 20 October 2021.
3. Efficacy assessments will not be performed and existing efficacy data will not be analyzed.

1. PROTOCOL SUMMARY

1.1. Synopsis

Study Title: A Phase 2b/3 Open-label Trial of VTS-270 (2-hydroxypropyl- β -cyclodextrin) in Subjects With Neurologic Manifestations of Niemann-Pick Type C1 Disease Previously Treated Under Protocol VTS301

Protocol Number: VTS-270-302	Type: Interventional - Phase 2b/3
Condition/Disease: Neurologic Manifestations of Niemann-Pick Type C1 (NPC1) Disease	
Approximate Number of Subjects: 7	Approximate Duration of Subject Participation: Up to 3 years (Note: the last day of study drug administration can be no later than 20 October 2021. A follow-up visit will be conducted after that date.)

Rationale:

At present, there are no therapies approved for use in the United States (US) for subjects with NPC1 disease. Miglustat (Zavesca[®]), an imino sugar, has been approved for the treatment of subjects with NPC1 disease in many countries outside the US, including the European Union; off-label use in the US is available. The efficacy of Miglustat is modest at best, and development of effective treatments for NPC1 is required to address the significant unmet need for this fatal disease.

This study is designed to enable subjects who have completed the treatment phase of Study VTS301 with an assessment by the treating principal investigator (PI) of Study VTS301 of continued benefit to have continued treatment with adrabetadex (VTS-270) and consensus of the PI in this study. A completer is defined as a subject who has completed Visit 27/Week 52 or completed at least through Visit 13/Week 24 and required rescue option, and is continuing in Part C of Study VTS301. Subjects will enter this study at the same dose and regimen they were taking upon exiting Study VTS301.

Objectives and Endpoints:

Primary Objective	Endpoints
To evaluate the long-term safety and tolerability of adrabetadex in subjects transitioning from Study VTS301.	Primary baseline values are collected from the first assessment gathered in the Study VTS301, which is before the first dose of adrabetadex in Study VTS301. Baseline values of the current study at Visit 1 are from evaluations gathered within the study period of Study VTS302 to account for newer raters in the study. These values will reflect evaluations by the Primary Investigator of the current study, performed within the study sites described in the Overall Design . Endpoints will be assessed at Weeks 26, 52, 78, 104, 130, and/or 156 (end of study). (Note: The last possible date of treatment is 20 October 2021. A follow-up visit will be conducted after that date.) Summary of general safety profile, including adverse events (AEs) (serious and nonserious), vital signs, change in annual weight, and laboratory parameters.

Adrabetadex Solution for Injection
Protocol VTS-270-302 Amendment 2 Version 2

Study Title: A Phase 2b/3 Open-label Trial of VTS-270 (2-hydroxypropyl- β -cyclodextrin) in Subjects With Neurologic Manifestations of Niemann-Pick Type C1 Disease Previously Treated Under Protocol VTS301

Overall Design:

This is a multicenter, multinational, open-label study of adrabetadex, with intrathecal (IT) administration by lumbar puncture (LP) every 2 weeks. To qualify for participation in this study, subjects will have participated in Study VTS301 and completed the treatment phase of the study, with an assessment by the treating PI in Study VTS301 of continued benefit to treatment with adrabetadex and consensus of the PI in Study VTS-270-302. A completer is defined as a subject who has completed Visit 27/Week 52 or completed at least through Visit 13/Week 24 and required rescue option, and is continuing in Part C of Study VTS301.

Eligible subjects who transition into this study will receive treatment with adrabetadex at the last dose level administered in Study VTS301, administered IT via LP infusion every 2 weeks, for up to a total duration of 3 years or until the investigator considers adrabetadex to be no longer beneficial to the subject, or the adrabetadex development program is discontinued.

Number of Subjects:

Approximately 7 subjects who travelled and/or relocated to participate in Study VTS301 and who continue to have benefit from adrabetadex treatment, and are willing to continue treatment and observation at a study center that is in closer proximity to where they reside. Any country may serve as a location for an activated study site, including but not limited to Costa Rica, Mexico, and China.

Treatment Groups and Duration:

All subjects will receive adrabetadex. The total duration of subject participation is up to 3 years or until the investigator considers adrabetadex to be no longer beneficial to the subject or the adrabetadex development program is discontinued.

1.2. Schedule of Study Events

Table 1: Schedule of Study Events

	Visit 1 (Baseline of Current Study)	Visits Occur Every 2 Weeks Starting From Visit 2 (Week 2) Until the End of the Study at Visit 79 (Week 156) ^q	Unscheduled Visit
Window (days)	(+14)	Window for Visits 2 to 6 (Weeks 2 to 10) ± 3 days; for all other visits ± 7 days	
Time Point (Week)	0	Week 2 to Week 156 (every 2 weeks)	
Study Procedure			
Informed consent ^a	X		
Review eligibility	X		
Demographics, medical history ^b	X		
Medication history	X		
Current medical condition ^c	X	X	X
Collect urine ^d	X	Every 6 months starting from Visit 14 (Week 26)	X
Pregnancy test ^e	X	Every 6 months starting from Visit 14 (Week 26)	
Physical examination ^f	X	Every 6 months starting from Visit 14 (Week 26)	X
Vital signs	X ^{g,h}	X ^{f,g}	X ^{f,g}
Weight and height ⁱ	X	Every 12 months until end of study Visit 79 (Week 156)	
Neurological examination ^j	X	Every 6 months starting from Visit 14 (Week 26)	
Clinical laboratory testing ^k	X	Every 6 months starting from Visit 14 (Week 26)	

Adrabetadex Solution for Injection
 Protocol VTS-270-302 Amendment 2 Version 2

	Visit 1 (Baseline of Current Study)	Visits Occur Every 2 Weeks Starting From Visit 2 (Week 2) Until the End of the Study at Visit 79 (Week 156) ^a	Unscheduled Visit
Window (days)	(+14)	Window for Visits 2 to 6 (Weeks 2 to 10) ± 3 days; for all other visits ± 7 days	
Time Point (Week)	0	Week 2 to Week 156 (every 2 weeks)	
Audiologic testing ^{b,m}	X	Every 6 months starting from Visit 14 (Week 26)	
ABR ^b	X	Do not perform starting 20 January 2021 (implemented in advance of amendment 2, as there is a direct impact to subject safety)	
Clinician-CGIC	X	Do not perform starting 10 February 2021	
NPC-SS intake	X	Do not perform starting 10 February 2021	
EQ-5D-3L ^b	X	Do not perform starting 10 February 2021	
Lumbar puncture and study drug administration ^{b,o}	X	X	X
AEs ^p	X	X	X
Concomitant medications	X	X	X

^a Baseline Visit only (and at times as may be required by the study or when changes are made to the consent form).

^b Medical history includes history of NPC1 disease, diagnosis date, and prior treatments.

^c Assessment of current medical condition will be obtained from the last visit of Study VTS301 Part C. Current medical condition will only be recollected if the assessment from Study VTS301 exceeds 12 weeks from Visit 1 (Baseline of Current Study).

^d Urine will be obtained for urinalysis only. If completed in Study VTS301 within the past 12 weeks, it does not need to be repeated.

^e Urine pregnancy test at Baseline of the Current Study Visit (Visit 1) and every 6 months except at final visit, which should be a serum pregnancy test.

^f Full physical examination at Baseline of the Current Study Visit (Visit 1); abbreviated physical examination at all other visits. If a full physical examination is completed in Study VTS301 within the past 12 weeks, it does not need to be repeated. ECG assessment is to be performed annually.

^g Vital signs, including blood pressure, will be recorded following a 5-minute rest in a supine position.

^h A second set of vital signs will be recorded following recovery of sedation from lumbar puncture procedure.

Adrabetadex Solution for Injection
Protocol VTS-270-302 Amendment 2 Version 2

ⁱ Height is to be measured once at the Baseline of Current Study Visit (Visit 1).

^j Full neurological examination at the Baseline Visit and End of Study Visit; abbreviated neurological examination at all other visits.

^k Clinical laboratory tests include chemistry, hematology, and coagulation. If completed in Study VTS301 within the past 12 weeks, it does not need to be repeated.

^l If audiology and ABR were obtained at Study VTS301 site within 12 weeks of the Baseline of the Current Study Visit (Visit 1), it does not have to be repeated.

^m If a subject reports an increase in clinically significant hearing impairment at any post-baseline assessment, unscheduled audiologic evaluation visits will increase in regularity at the discretion of the Primary Investigator.

ⁿ If the subject is unable to provide feedback for the EQ-5D-3L assessment, a parent or legal guardian can serve as proxy. The same parent or legal guardian from Study VT301 should make their best attempt to serve as proxy for all EQ-5D-3L assessment visits in the current study.

^o All procedures must be completed prior to first dose of study drug.

^p The collection period of AEs will begin after informed consent is obtained and end after procedures for the final study visit have completed.

^q End of Study and Follow-up Visit should follow the procedures detailed in [Table 2](#).

Table 2: End of Study and Follow-up from Last Dose

	EOS	Follow-up Visit^a
Window (days)		(±14)
Time Point (Week)		EOS+2W
Study Procedure		
Adverse events	X	X
Concomitant medications	X	X
Audiologic testing ^b	X	-
Complete physical exam	X	-
Vital signs ^c	X	-
Clinical laboratory testing ^d	X	-
Complete Neurological examination	X	-
Urine Pregnancy Test	X	-

EOS = End of Study; W = weeks.

^a The follow-up visit is required for all subjects who complete their final dose of treatment or undergo early termination from the study. The visit may be conducted over the telephone.

^b If a subject reports an increase in clinically significant hearing impairment at any post-baseline assessment, unscheduled audiologic evaluation visits will increase in regularity at the discretion of the Primary Investigator.

^c Vital signs, including blood pressure, will be recorded following a 5-minute rest in supine position.

^d Clinical laboratory tests include chemistry, hematology, and coagulation.

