3. OBJECTIVES AND ENDPOINTS

3.1. Primary Objective(s)/Endpoint(s)

Primary Objective	Endpoint
To evaluate the long-term safety and tolerability of adrabetadex in subjects transitioning from Study VTS301.	
Primary baseline values are collected from the first assessment gathered in the Study VTS301, which is before the first dose of adrabetadex in Study VTS301.
 
Baseline values of the current study at Visit 1 are from evaluations gathered within the study period of Study VTS302 to account for newer raters in the study. These values will reflect evaluations by the Primary Investigator of the current study, performed within the study sites described in the Overall Design.
 
Endpoints will be assessed at Weeks 26, 52, 78, 104, 130, and/or 156 (end of study) (Note: The last possible date of treatment is 20 October 2021. A follow-up visit will be conducted after that date.)
 
Summary of general safety profile, including AEs (serious and nonserious), vital signs, change in annual weight, and laboratory parameters.

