4.2. Study Design Rationale

Adrabetadex is being developed for pediatric use. The typical onset of NPC symptoms is in early childhood. Owing to different clinical presentations and course of disease, NPC is typically categorized as early-infantile onset (less than 2 years of age), late-infantile onset (2 to less than 6 years of age), juvenile onset (6 to less than 15 years of age) and adolescent/adult onset (at least 15 years of age).

Due to the shorter life-span (death is usually within 5 years for early-infantile onset and between 7 and 12 years for late-infantile onset), and the difficulty in making a diagnosis in those subjects with infantile onset forms of NPC, the focus of this drug development program has been for those 4 to 21 years of age with onset of neurologic symptoms before the age of 15. The disease has a relatively slow progression in those with adult onset.

This study is being conducted with the goal of obtaining longitudinal safety and efficacy data; as of the approval of Amendment 2, only safety data will be collected.

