5.2. Exclusion Criteria

A subject is ineligible for study participation if, at the Baseline Visit:

1. Subjects discontinued from Study VTS301 for AEs or perceived lack of efficacy.
2. Subject has an unresolved SAE for which treatment with adrabetadex has been halted.
3. Female subjects who are pregnant or nursing.
4. Subjects with suspected infection of the central nervous system or any systemic infection.
5. Subjects with a spinal deformity that could impact the ability to perform a LP.
6. Subjects with a skin infection in the lumbar region within 2 months of study entry.
7. Any of the following laboratory abnormalities at the Baseline Visit:
 - a. Neutropenia, defined as an absolute neutrophil count of less than $1.5 \times 10^9/L$.
 - b. Thrombocytopenia (platelet count of less than $75 \times 10^9/L$).
 - c. Activated partial thromboplastin time or prothrombin time prolonged by greater than $1.5 \times$ the upper limit of normal (ULN) or known history of a bleeding disorder.
 - d. Aspartate aminotransferase or alanine aminotransferase (ALT) greater than $4 \times$ ULN.

- e. Anemia: hemoglobin greater than 2 standard deviations below normal for age and gender.
- f. Estimated glomerular filtration rate less than 60 mL/minute/1.73 m² calculated using the modified Schwartz formula ([Schwartz, 2009](#)) for subjects aged 4 through 17 years old or using the Chronic Kidney Disease Epidemiology Collaboration equation formula for subjects aged 18 years or older.
8. Evidence of obstructive hydrocephalus or normal pressure hydrocephalus.
9. Recent use of anticoagulants (in past 2 weeks prior to first dose [Study Day 0]).
10. Active pulmonary disease, oxygen requirement, or clinically significant history of decreased blood oxygen saturation, pulmonary therapy, or requiring active suction.
11. Subjects who, in the opinion of the investigator, are unable to comply with the protocol or have medical conditions that would potentially increase the risk of participation.

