8.2.4. Weight and Height

Weight and height will be collected as outlined in the Schedule of Study Events ([Table 1](#)). Any change from the Primary Baseline Visit in subject weight that is considered by the investigator to be clinically significant will be recorded as an AE.

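### The End of Study visit takes no weight, although annual weight change is part of the primary safety endpoint and dosing ends on a calendar date

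*Combined protocol and SAP*

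**What the plan says.** Section 3.1 (and the synopsis) gives one primary endpoint: "Summary of general safety profile, including AEs (serious and nonserious), vital signs, change in annual weight, and laboratory parameters". Sections 3.2 and 3.3 state that there are no secondary or exploratory objectives. Section 3.1 defines two baselines: the Primary Baseline, taken before the first adrabetadex dose in VTS301, and Visit 1 of the present study.

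Table 1 (section 1.2) has a joint row for weight and height, taken at Visit 1 and then "Every 12 months until end of study Visit 79 (Week 156"). Footnote i to that row says "Height is to be measured once at the Baseline of Current Study Visit (Visit 1"). Footnote q refers the End of Study and Follow-up visits to Table 2.

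Table 2 lists adverse events, concomitant medications, audiology, complete physical and neurological examinations, vital signs, laboratory tests and a pregnancy test at End of Study. It does not list weight. Neither does the End of Study list in section 7.1.1, the content of the complete physical examination in section 8.2.3, or the definition of vital signs in section 8.2.5.

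Section 8.2.4 refers back to Table 1 and adds an adverse event rule: "Any change from the Primary Baseline Visit in subject weight" becomes an adverse event if the investigator judges it clinically significant. Section 9.3.2 says that adverse events and other safety data will be listed. No section mentions weight-for-age, percentiles, z-scores or BMI.

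On age, section 4.2 states that "the focus of this drug development program has been for those 4 to 21 years of age", limited to patients whose neurologic disease began before they were 15. The eGFR criterion in section 5.2 also provides for subjects aged 18 or older.

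**The concern.** A change endpoint needs a value at the end of the exposure it describes. Weight is tied to anniversaries of Visit 1, whereas treatment ends on a calendar date or earlier by choice (section 7.1). Most subjects will therefore stop between anniversaries, and the visit that closes their treatment does not weigh them. A subject who stops before Week 52 has no post-baseline weight in this study at all.

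There is also a problem of interpretation. In a child, an unchanged weight over a year is not a neutral result. The plan lists weight with no growth reference, so failure to gain can look like stability. With about 7 subjects and listings only, the individual listed values are all the evidence on this component, so each should be complete and readable.

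**Working it through.** The plan gives no figure for weight to reproduce. The check is of the schedule, followed by an illustration of size.

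**1. Schedule.** Visit *v* falls at Week 2(*v* − 1). Visit 14 is Week 26 and Visit 79 is Week 156, as Table 1 states. Weights every 12 months fall at Weeks 0, 52, 104 and 156: at most four weights per subject, and one height.

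**2. Can anyone reach the Week 156 weight?**
- Original protocol date: 23 October 2018. Last permitted dose: 20 October 2021.
- Interval: 1093 days; 1093 / 7 = 156.1 weeks.
- Week 156 is 156 × 7 = 1092 days after Visit 1. To reach it by the cut-off, Visit 1 had to occur by 24 October 2018, one day after the protocol date. Using the 7-day visit window moves this to 31 October 2018.
- Ethics approval (section 10.1.1) and centre activation (section 6.2) come first, so the Week 156 weight is essentially unreachable.

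**3. How old can the last weight be?**
- Visits are every 2 weeks. A subject whose last visit is Week 102 was last weighed at Week 52: 102 − 52 = 50 weeks. With ±7 days at each end, this can reach 52 weeks, or about 12 months.
- Illustration, not a claim about any subject: for a Visit 1 on the date of Amendment 1 (3 December 2019), the cut-off falls at 98.1 weeks. Week 104 is not reached, and the Week 52 weight is 98.1 − 52 = 46.1 weeks old at the cut-off.

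**4. Is the End of Study visit held in person?** Table 2 requires a complete physical examination and laboratory tests there, so yes. The later Follow-up Visit may be held by telephone, so a weight cannot be relied on then.

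**5. Size of a hidden failure to gain.** The documents give no weights or growth rates. Assume a starting weight *W* of 20 to 30 kg and an expected gain *g* of 2 to 5 kg a year. If raw weight is unchanged after one year, the shortfall relative to expected weight is *g* / (*W* + *g*):
- *W* = 30, *g* = 2: 2/32 = 6.3%
- *W* = 20, *g* = 2: 2/22 = 9.1%
- *W* = 30, *g* = 5: 5/35 = 14.3%
- *W* = 20, *g* = 5: 5/25 = 20.0%

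For a fully grown subject *g* = 0 and nothing is hidden. The comparison with Primary Baseline covers more growth: entry requires at least Week 24 of VTS301 (section 5.1), so at least about 24 weeks have passed by Visit 1.

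**6. Table 1 against its footnote.** The row schedules height every 12 months, and footnote i allows it only once. Both cannot be followed. Weight-for-age needs only weight, age and sex. Repeat height is needed for BMI, or to separate poor linear growth from poor weight gain.

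**The case against.** The strongest reply is that little depends on this. Weight is one item in a general safety profile. The risks described in section 2.3 are ototoxicity, fatigue-like symptoms, balance disorders and pyrexia, not weight loss. About 7 subjects are listed with no test, no summary estimate and no control. Section 8.2.4 already lets the investigator record any clinically significant weight change as an adverse event, with no restriction to a fall in kilograms. Physical examinations are held every 6 months, and section 8.2 permits unscheduled assessments. Standardised weight could be derived later from data already held. The sponsor has already judged benefit/risk negative.

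Most of this stands, and it is why the point is minor. It does not supply the missing reading: an unscheduled weight is permitted but not required, and a weight not taken at End of Study cannot be recovered.

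A reader might go further and infer that growth masks weight loss, so that the endpoint cannot show harm. The documents do not support that. A real fall between two weighings appears as a fall. What can be hidden is failure to gain, or a loss regained before the next annual weight. Nor do the documents show that these subjects are mostly growing: 4 to 21 years is the programme's focus, not the age distribution here.

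A reader might also see repeat annual height as the main remedy. From Amendment 2 (10 February 2021) to the last permitted dose is 252 days, or 36 weeks, so it would add at most one annual height per subject.

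**Conclusion.** The schedule gap holds on the documents alone. A named component of the primary safety endpoint has no end-of-treatment value; the last weight can be up to about 12 months old when a subject stops; and the Week 156 weight is essentially unreachable. The conflict between the weight-and-height row and footnote i also holds.

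The growth point holds in a limited form: raw change can hide failure to gain in subjects who are still growing. The 6% to 20% of expected weight after one year rests entirely on the assumed weights and gains, and applies to an unknown number of subjects.

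A standardised weight would show a shortfall. With no control arm, it could not attribute the shortfall to drug or disease. Severity: minor.

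**What to change.** 1. Add weight, and height at the same in-person visit, to the End of Study column of Table 2 and to the list in section 7.1.1.
2. In section 9.3.2, state that age- and sex-standardised weight will be listed beside raw weight, with change from both the Primary Baseline and Visit 1, for subjects within the age range of the reference. Name the reference. List the date of each weight and the date of the last dose, so that the gap is visible.
3. Reconcile the 12-monthly weight-and-height row of Table 1 with footnote i, so that sites have one instruction on height.

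The cost is one extra set of readings at a visit already held and a reference-table calculation. Heights already missed cannot be recovered, and subjects who have already completed End of Study gain only the standardised listing.
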